2.3.4.1.2 Risks related to study treatment

SAR444245 has the potential to induce CRS which could exacerbate the manifestations of COVID-19 infection. It is, however, worth noting that pegylated IL-2 bempegaldesleukin is currently being evaluated for the treatment of patients with mild COVID-19 in a Phase 1b study (NCT04646044).

2.3.4.1.3 Risks related to study-related activity

It is important to minimize the risk of exposure of patients to COVID-19. In addition to the contingency measures described in [Section 10.9](#), the following prevention and mitigation plans could be implemented at clinical sites:

- All participating sites should have implemented measures according to regional/local Health Authorities, European Medicines Agency (EMA), ESMO, ASCO guidelines including but not limited to restrictions of access to the hospitals for visitors, physical distancing and personal protective equipment.
- Study participants should be treated in a dedicated area that is separated from patients with COVID-19 infection.

[figure not shown]
2.3.4.1.4 Conclusion on the benefit-risk pertaining to COVID-19

Overall, benefit-risk is deemed acceptable in patients with advanced and metastatic gastrointestinal cancer during the COVID-19 pandemic. The Sponsor will continue to evaluate benefit-risk during the study period.

3 OBJECTIVES AND ENDPOINTS

Table 1 - Objectives and endpoints

Objectives	Endpoints
Primary	
• To determine the antitumor activity of SAR444245 in combination with other anticancer therapies• Objective response rate (ORR) defined as the proportion of participants who have a confirmed complete response (CR) or partial response (PR) determined by Investigator per Response Evaluation Criteria in Solid Tumors (RECIST) 1.1 (1)
Secondary	
• To assess the safety of SAR444245 in combination with other anticancer therapies• To assess other indicators of antitumor activity• Incidence of treatment emergent adverse events (TEAEs), serious adverse events (SAEs), laboratory abnormalities according to National Cancer Institute Common Terminology Criteria for Adverse Events (NCI CTCAE) V5.0 and American Society for Transplantation and Cellular Therapy (ASTCT) consensus grading (2)• Time to response (TTR), defined as the time from the first administration of investigational medicinal product (IMP) to the first tumor assessment at which the overall response was recorded as PR or CR that is subsequently confirmed and determined by Investigator per RECIST 1.1• Duration of response (DoR), defined as the time from first tumor assessment at which the overall response was recorded as CR or PR that is subsequently confirmed until documented progressive disease (PD) determined by Investigator per RECIST 1.1 or death from any cause, whichever occurs first• Clinical benefit rate (CBR) including confirmed CR or PR at any time or stable disease (SD) of at least 6 months determined by Investigator per RECIST 1.1.• Progression-free survival (PFS), defined as the time from the date of first IMP administration to the date of the first documented disease progression determined by Investigator as per RECIST 1.1 or death due to any cause, whichever occurs first• Plasma concentrations and where applicable PK parameters of SAR444245• Incidence of anti-drug antibodies (ADAs) against SAR444245
Exploratory	

For China, please see [Section 10.7](#) for details.

3.1 APPROPRIATENESS OF MEASUREMENTS

Each of the efficacy and safety assessments chosen for use in this study is considered well established and relevant in gastrointestinal oncology study setting.

In addition, suitable steps have been built into each of these assessments to ensure their reliability and accuracy and to minimize any risks to participant safety.

4 STUDY DESIGN

4.1 OVERALL DESIGN

This is a Phase 2, multi-cohort, un-controlled, non-randomized, open-label, multi-center study assessing the antitumor activity and safety of SAR444245 combined with other anticancer therapies in participants with advanced or metastatic gastrointestinal cancer.

This study is developed as a master protocol in order to accelerate the investigation of SAR444245 with various anticancer therapies by identifying early efficacy signals. This design is with the flexibility to open new treatment cohorts as new treatment combinations become available and close existing treatment arms that demonstrate minimal clinical activity or unacceptable toxicity.

The information that is introductory and common to all cohorts is included in the present document (“Master Protocol”), and cohort-specific elements are included in separate substudies. This study is designed with the flexibility to open new treatment arms or add new indications as permitted by scientific rationale.

A graphical presentation of the study schema is shown in the individual substudy.

Interactive Response Technology (IRT) will be used to control recruitment, assignment per site and to facilitate the handling, management, and accountability of drug supply.

The duration of the study for a participant will include:

- **Screening Period:** up to 28 days
- **Treatment Period:** enrolled participants will receive continuous treatment until progressive disease (PD), unacceptable adverse event (AE) or other full permanent discontinuation criteria as described in [Section 7](#); or completion of Cycle 35 (if applicable).
- **End of Treatment and Follow-up:** End of Treatment Visit will occur 30 days \pm 7 days from last IMP administration or prior to initiation of further therapy, whichever comes first. Participants will then enter the **Observation Period** and will be followed differently depending on the reason leading to **End of Treatment (EOT)**.
 1. Participants who discontinue study treatment **without PD** or who **complete 35 cycles of treatment without PD** will be followed every 3 months \pm 7 days from last IMP administration, for safety (as per Schedule of Activities [SoA]) and tumor imaging assessments until PD, start of another anticancer therapy, final cohort cut-off, whichever comes first, before moving to the Survival Phone Call Follow-Up Period.
 2. Participants who discontinue study treatment **with PD** will be followed for safety in the Follow-Up Visit 1 occurring 3 months \pm 7 days from last IMP administration, before moving to the Survival Phone Call Follow-Up Period.

Participants who move into the **Survival Phone Call Follow-Up Period** will be contacted by telephone every 3 months \pm 14 days to assess for survival status. Updated survival status may be requested by the Sponsor at any time during the study. Survival Phone Call Follow-up will continue until death, participant request to discontinue from follow-up, or cut-off date for the given cohort final analysis has been reached, or upon cancellation of Survival follow-up in the given cohort at the discretion of the Sponsor at any prior timepoint whichever occurs first.

The cohort cut-off for the primary ORR endpoint analysis for each individual cohort is estimated to be approximately 9 months from the date of the last participant first infusion. This would allow the possibility to observe the response of the last participant for 6 months, assuming there is a response at first treatment assessment.

After the cohort cut-off date for the primary ORR analysis, participants can continue to receive IMP, if clinical benefit is observed, until full permanent discontinuation criteria described in **Section 7** are met and will continue to undergo all assessments as per the study schedule of activities.

For each cohort, the cut-off date for the final analysis (ie, analysis of secondary objectives and update of primary objective) will be 18 months from the corresponding cohort LPI. After this cut-off date for the final analysis, the participants of the given cohort still receiving study treatment in that specific cohort will be followed up as the cohorts after early termination described in **Section 10.1.9**.

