Cycle Day (Visit window in Days)	D-28 to D-1	D1	D8 ^f (±1)	D15 ^f (±1)	D1 (±3)	30 days (+/- 7 days) after last IMP or at initiation of further therapy	3 months after last IMP admin ±7 days	6 months after last IMP admin ±7 days	Every 3 months after FU visit 2 ± 7 days	Every 3 months +/- 14 days		
Urinalysis ^g	X	X			X	X	X				See Section 10.2	
IMP												
SAR444245		X			X							
Hospitalization ^h		X										
AE/SAE assessment ^k	X	Continuously throughout treatment period					X				See Section 8.3	
Prior/Concomitant Meds	X	Continuously throughout treatment period									See Section 6.8	
First subsequent anti-cancer therapy						X	X	X	X	X		
Survival status										X		
Pharmacokinetic (PK) / Pharmacodynamic (PDy) / Immunogenicity assessments												
PK SAR444245	See PK flowcharts in Section 1.5.1 and Section 1.5.2											
ADA SAR444245	See PK flowcharts in Section 1.5.1 and Section 1.5.2											
PDy - Blood and tumor tissue collection ^{l,m}	See Biomarker Flowchart in Section 1.4											
Tumor assessment												
Brain imaging ⁿ	X										See Section 8.1	
CT/MRI ^o	X				X	X	X	X	X		See Section 8.1	

- a Evaluation: Screening assessments to be performed prior to first IMP administration unless otherwise indicated. There is no need to perform Cycle 1 Day 1 laboratory assessments that have been performed as part of screening within 3 days prior to first IMP administration. During the study treatment period, all assessments must be performed, and results should be reviewed by the investigator prior to IMP administration at that visit. After Cycle 1, samples for laboratory assessments (excluding PK & biomarker) can be collected up to 3 days prior to IMP administration. ICF must be signed before any study-specific procedures are performed and can be signed more than 28 days prior to first IMP administration. Screening time indicates the maximum time frame relative to the first IMP administration in which study procedures used to support eligibility are done.
- b Cycle: a treatment cycle is 21 days. See details in [Section 6.1](#) for IMP administration. If treatment cycles are adjusted, all procedures except tumor assessment imaging will be completed according to the cycle number. Tumor assessment imaging will be performed at fixed time points from C1D1 regardless of any treatment delays.

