- o CT/MRI: The initial tumor imaging will be performed within 28 days prior to C1D1. Scans performed as part of routine clinical management are acceptable for use as the screening scan if they are of diagnostic quality and performed within 28 days prior to the date of enrollment. On study imaging will be performed every 9 weeks (63 ± 7 days) after the date of first IMP and if clinically indicated. Imaging studies should follow calendar days and should not be adjusted for delays in cycle starts or extension. The same imaging technique should be used in a participant throughout the trial. After week 45, tumor imaging should be performed every 12 weeks (84 ± 7 days). CT scan of the chest, abdomen, pelvis and any other locations with suspicion or evidence of disease involvement is required for the baseline assessment, during treatment period until PD. Per the primary tumor assessment criteria, after the first documentation of response or the first documentation of progression (if the participant is clinically stable), confirmatory imaging may be performed no fewer than 28 days later. Alternately, the scan performed at the next scheduled time point (eg, every 63 ± 7 days) may be used as confirmation. Tumor assessment is not needed for participants who start another anti-cancer therapy.

Abbreviations: ADA=anti-drug antibodies; AE=adverse event; AST=aspartate transaminase; ALT=alanine transaminase; C=Cycle; ANC=Absolute neutrophil count; AP=Alkaline phosphatase; BUN=Blood urea nitrogen; CRF=case report form; CRS=Cytokine release syndrome; CT=computed tomography; [REDACTED]; D=Day; ECG=electrocardiogram; ECOG=Eastern Cooperative Oncology Group; e-CRF=electronic case report form; EOT=end-of-treatment; FT4=free thyroxine; FU=follow-up; HBsAg=Hepatitis B surface antigen; HCV=Hepatitis C virus; ICF=Informed consent form; IMP=investigational med [REDACTED] ed ratio; LDH=Lactate hydrogenase; LVEF=left ventricular ejection fraction; MRI=magnetic resonance imaging; MUGA= multigated acquisition; PD=progressive disease [REDACTED] PDy=pharmacodynamic; PK=pharmacokinetic; PR=partial response; PS=Performance Status; SpO2= oxygen saturation; Q3W=every 3 weeks; RECIST=Response Evaluation Criteria in Solid Tumors; SAE=serious adverse event; T3=tri-iodothyronine; TSH=thyroid stimulating hormone; WBC=White blood cells.

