9.4.3.3 Clinical benefit rate

The CBR will be defined as the proportion of participants with clinical benefit (confirmed CR or PR as BOR, or SD lasting at least 6 months). Specifically, participants will be considered as clinical benefit responders if they achieve a CR or PR as BOR, or have an overall response recorded as SD at 6 months (ie, 26 weeks) or later from first IMP intake, allowing for the ± 7 days visit window for tumor assessment scheduled at 27 weeks.

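### After treatment stops without PD, the protocol sets two different tumor-imaging calendars, so the 26-week clinical benefit rate depends on the date of the last dose

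*Protocol*

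**What the plan says.** Two timing rules cover the same scans in the master protocol.

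- **Counted from the last dose.** Section 4.1, repeated in the synopsis (1.1), follows participants who stop without PD, or who complete 35 cycles without PD, every 3 months "from last IMP administration, for safety (as per Schedule of Activities [SoA]) and tumor imaging assessments until PD, start of another anticancer therapy" or final cohort cut-off. In the SoA (1.3) the CT/MRI row is marked at end of treatment (EOT) and at the follow-up visits, the first of which is timed "3 months after last IMP admin ±7 days".
- **Counted from the first dose.** SoA footnote b: "Tumor assessment imaging will be performed at fixed time points from C1D1 regardless of any treatment delays". Footnote o, which is attached to that same CT/MRI row: "On study imaging will be performed every 9 weeks (63 ± 7 days) after the date of first IMP and if clinically indicated", changing to every 12 weeks after week 45, with the added rule "Imaging studies should follow calendar days and should not be adjusted for delays in cycle starts or extension". Section 8.1.1 repeats this calendar. The only exemption it states is the start of another anticancer therapy. The substudy 01 SoA repeats the same text in its footnotes b and p.

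Section 9.4.3.3 counts a participant as having clinical benefit if best response is CR or PR, or if SD is recorded at 26 weeks or later from first dose. It allows for the ±7-day "visit window for tumor assessment scheduled at 27 weeks". Sections 9.4.3.2 and 9.4.3.4 date progression for DoR and PFS at its first documentation.

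**The concern.** A site with a participant who has stopped for toxicity and has not progressed can follow either calendar and point to text that supports it. Sites may therefore image comparable participants on different dates.

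The CBR rule makes this more than an editorial matter. Its 26-week threshold is counted from first dose, and its window is built around a scan that only the first-dose calendar guarantees. If imaging moves to the last-dose clock, whether SD counts depends partly on when treatment stopped and not only on how long the disease stayed stable. PFS and DoR are also exposed in principle, because progression is dated at the scan that finds it.

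**Working it through.** **Inputs from the protocol.** Cycle length 21 days; imaging every 63 days from first dose to week 45, then every 84 days; EOT visit 30 ± 7 days after last dose; follow-up imaging every 3 months ± 7 days from last dose; CBR threshold 26 weeks = 182 days from first dose.

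**The plan's own figure.** The third scan on the first-dose calendar is at 3 × 63 = 189 days = week 27. With the window, 189 − 7 = 182 days = week 26. The CBR rule is therefore consistent with the first-dose calendar.

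**The Section 4.1 calendar.** Take one month as 30.44 days, so 3 months = 91.3 days = 13.0 weeks and 30 days = 4.3 weeks. With last dose in Cycle k and no cycle delays, the last dose is at week 3(k − 1). Scans follow the 9-weekly grid up to that date, then last dose + 4.3 (EOT), + 13.0, + 26.1 weeks, and so on.

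| Last dose | Scans after last dose (week) | First scan at or after week 26 | Versus week 27 |
|---|---|---|---|
| C1, week 0 | 4.3, 13.0, 26.1 | 26.1 | −0.9 |
| C2, week 3 | 7.3, 16.0, 29.1 | 29.1 | +2.1 |
| C3, week 6 | 10.3, 19.0, 32.1 | 32.1 | +5.1 |
| C4, week 9 | 13.3, 22.0, 35.1 | 35.1 | +8.1 |
| C5, week 12 | 16.3, 25.0, 38.1 | 38.1 | +11.1 |
| C6, week 15 | 19.3, 28.0 | 28.0 | +1.0 |
| C7, week 18 | 22.3, 31.0 | 31.0 | +4.0 |
| C8, week 21 | 25.3, 34.0 | 34.0 | +7.0 |
| C9, week 24 | 28.3, 37.0 | 28.3 (37.0 without the EOT scan) | +1.3 |
| C10 or later | – | 27.0 | 0 |

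**Effect of the visit windows.** A Cycle 5 stop can be rescued if the 3-month scan is a week late (25.0 + 1 = 26.0). A Cycle 8 stop can be rescued if the EOT scan is a week late (147 + 37 = 184 days, past 182). Cycle 3 and 4 stops cannot: 19.0 + 1 = 20.0 and 22.0 + 1 = 23.0.

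**Size for CBR.** The protocol gives no progression rate off treatment, so this step rests on an assumption: exponential time to PD after stopping, with median m of 3, 6 or 9 months. For a last dose in Cycle 4 (day 63), the chance of being PD-free at the qualifying scan is 0.5 raised to (days from last dose to scan)/(30.44m). That is 189 − 63 = 126 days on the first-dose calendar and 2 × 91.3 = 182.6 days under Section 4.1.

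- m = 3: 0.38 versus 0.25
- m = 6: 0.62 versus 0.50
- m = 9: 0.73 versus 0.63

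In a cohort of 40 (the Cohort A size), each reclassified participant moves CBR by 1/40 = 2.5 percentage points.

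**Size for PFS and DoR.** Simulating under the same assumption, for last doses in Cycles 2 to 8, documented PD comes later under Section 4.1 by a mean of 0.2 to 1.0 weeks if the EOT scan is done, and 1.2 to 2.7 weeks if it is not. I do not use the simulated medians: the assumed medians of 3, 6 and 9 months fall exactly on the 3-monthly scan dates, which makes them an artefact. After week 45 the comparison is 12 against about 13 weeks, close to nil.

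**The case against.** The strongest reply is that the passages can be harmonised, in either of two ways.

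- **Separate clocks.** SoA footnote c lets follow-up assessments take place at the tumor-assessment visit, which presupposes that imaging has its own dates. Section 4.1 refers to the SoA, and Section 7.1.1 sends assessments after discontinuation back to it. On this reading Section 4.1 sets visit frequency and footnote o governs scans.
- **Separate phases.** Footnote b speaks of treatment delays, and part of footnote o speaks of cycle starts and the treatment period, so Section 4.1 could govern once treatment ends.

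Each is arguable, but the protocol states neither and they lead to different scan dates. The first is what the fix would make explicit. The second leaves the CBR rule resting on a scan that is no longer scheduled. It is therefore fair to call this unresolved wording, and too strong to say that the SoA is purely a first-dose calendar, since the SoA carries both anchors.

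Three stronger readings are tempting and are not supported.

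- *That PFS and DoR are materially inflated.* Comparing bare 9- and 13-week intervals suggests that the mean detection lag rises from 4.5 to 6.5 weeks. That ignores the EOT scan, after which the gap to the next scan is 13.0 − 4.3 = 8.7 weeks. Section 7.1.1 also asks for a repeat tumor assessment at discontinuation if none was done at the last cycle, and footnote o allows scans when clinically indicated.
- *That nobody who stops early has a scan near week 27.* Stops at Cycles 1, 6 and 9 give weeks 26.1, 28.0 and 28.3, and stops from Cycle 10 have the week-27 scan itself.
- *That the trial's main conclusion is at risk.* No claim is made here about the primary ORR. Section 9.4.1 makes the 90% intervals descriptive, and Section 9.1 states that no hypothesis is tested.

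The affected group is also narrow. For CBR it comprises participants who fully stop before about week 27 without PD, new therapy or a confirmed response. Under Section 6.5.1 of substudy 01, stopping one component does not end treatment if the other continues.

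**Conclusion.** The protocol gives two imaging calendars for participants who stop without PD and does not say which applies. Followed as written, Section 4.1 puts the first scan that can qualify SD for CBR anywhere from about week 26 to week 38 by stop date alone, against week 27 for everyone on the first-dose calendar. The clearest cases are Cycle 3 and 4 stops, which need about 5 and 8 further progression-free weeks and which the visit window cannot rescue. Neighbouring cycles are affected less, or can be rescued by the window.

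The scan dates are calendar arithmetic and assume no cycle delays. The CBR probabilities and the PFS and DoR delays also depend on the assumed exponential progression times. The effect on PFS and DoR is small with the EOT scan, moderate at most without it, and negligible after week 45. The protocol does not give the share of participants who stop without PD, so no cohort-level bias can be stated. This is a modest defect in a secondary endpoint, worth correcting because the correction is cheap.

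**What to change.** In the synopsis (1.1), Section 4.1 and the SoA follow-up columns, separate the two clocks:

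- safety follow-up visits stay every 3 months from the last dose, as now;
- tumor imaging stays on the first-dose calendar already stated in SoA footnotes b and o and Section 8.1.1, on or off treatment, until PD, new anticancer therapy or final cohort cut-off.

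Carry the same wording into the substudy SoA tables that repeat these rows and footnotes. Section 9.4.3.3 then needs no change, because its week-27 scan is scheduled for every participant still in imaging follow-up.

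The cost is protocol wording, plus possibly one or two more or earlier scans in participants who stop before week 45 without PD.

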4.2 SCIENTIFIC RATIONALE FOR STUDY DESIGN

The proposed study aims to establish proof-of-concept that combining the non-alpha-IL2 SAR444245 with other anticancer therapies will result in a significant increase in the percentage of participants experiencing an objective response.

The design of the study is a non-randomized study where the experimental combination will be assessed in a single cohort for each indication, using historical data for single agent as a benchmark to show outstanding ORR. The ORR will be assessed using RECIST 1.1 for participants with advanced and metastatic gastrointestinal cancer. The objective response will be assessed per Investigator as primary endpoint. Central imaging reading may be done retrospectively if significant activity is observed.

4.2.1 Participant input into design

There was no participant involvement in the design of the trial.

4.3 JUSTIFICATION FOR DOSE

Dose escalation for SAR444245 monotherapy and in combination with pembrolizumab or cetuximab is ongoing in the first-in-human HAMMER study. Data from a total of 68 patients who have received SAR444245 Q2W or Q3W in monotherapy, in a Q3W regimen in combination with pembrolizumab 200 mg Q3W, or with cetuximab 400/250 mg/m² QW is available as of 18 June 2021. SAR444245 24 μ g/kg Q3W pembrolizumab combination and cetuximab combination dose level have been cleared by HAMMER Safety Review Committee based on this data cut-off.

The dose levels tested to date for SAR444245 monotherapy administered using a Q3W schedule are 8 $\mu\text{g}/\text{kg}$ (n=4), 16 $\mu\text{g}/\text{kg}$ (n=6), 24 $\mu\text{g}/\text{kg}$ (n=11), 32 $\mu\text{g}/\text{kg}$ (n=6) and 40 $\mu\text{g}/\text{kg}$ (n=2).

In combination with pembrolizumab, SAR444245 has been administered Q3W at the doses of 8 $\mu\text{g}/\text{kg}$ (n=4), 16 $\mu\text{g}/\text{kg}$ (n=9), 24 $\mu\text{g}/\text{kg}$ (n=6), 32 $\mu\text{g}/\text{kg}$ (n=1). In combination with cetuximab, SAR444245 has been administered Q3W at 16 $\mu\text{g}/\text{kg}$ (n=5) or 24 $\mu\text{g}/\text{kg}$ (n=5).

For monotherapy cohort, the only DLT observed to date is a Grade 3 infusion reaction (occurred in C2D1 which resolved on the same day with supportive care) reported in a patient on 32 $\mu\text{g}/\text{kg}$ Q3W monotherapy.

For SAR444245 in combination with pembrolizumab 200 mg Q3W, 1 DLT (Grade 3 liver enzyme elevation with Grade 2 bilirubin elevation meeting drug-induced liver injury [DILI] criteria occurred in C1D1 which resolved after 7 days with steroids) was observed in a participant with SAR444245 24 $\mu\text{g}/\text{kg}$ Q3W with pembrolizumab.

No DLTs were reported by SAR444245 cetuximab combination cohort (SAR444245 24 $\mu\text{g}/\text{kg}$ Q3W).

Grade 3/4 TEAEs commonly reported by participants who received SAR444245 24 $\mu\text{g}/\text{kg}$ monotherapy (n=11) include in particular Grade 4 lymphocyte count decreased/lymphopenia (7 participants, 63.6%), Grade 3 anemia (3 participants, 27.3%), and Grade 3 dyspnea (2 participants, 18.2%). Of note, transient lymphocyte count decrease in the peripheral blood is an expected effect, consequence of T cell activation and temporary compartmental redistribution after IL-2 treatment. Nevertheless, this phenomenon can be reported as an adverse event (AE) in HAMMER study.

Grade 3/4 TEAEs reported by participants who received SAR444245 24 $\mu\text{g}/\text{kg}$ in combination with pembrolizumab (n=6) include Grade 4 lymphocyte count decreased (3 participants, 50.0%), Grade 3 aspartate aminotransferase (AST), alanine aminotransferase (ALT) & gamma-glutamyl transferase (GGT) increased (2 participants each for AST & ALT increased, 33.3%; 1 participant for GGT increased, 16.7%), Grade 3 blood phosphorus decreased & hypophosphatemia (1 participant each, 16.7%), and Grade 3 dyspnea (1 participant, 16.7%).

Grade 3/4 TEAEs reported by participants who received SAR444245 24 $\mu\text{g}/\text{kg}$ in combination with cetuximab (n=5) include Grade 3 chills (1 participant, 20.0%) and Grade 3 abdominal pain and vomiting (1 participant for each, 20.0%).

Only 1 Grade 4 CRS with Grade 3 hypertension, Grade 2 fever, and Grade 2/3 neurological symptoms (with 24 $\mu\text{g}/\text{kg}$ Q3W, 2.6%) is reported among participants who received SAR444245 monotherapy (n=38). From participants who received SAR444245 pembrolizumab combination (n=20), Grade 3 CRS (with 16 $\mu\text{g}/\text{kg}$ Q3W) is observed in 1 participant (5.0%) with Grade 3 hypotension and Grade 2 fever.

According to literature, prophylactic hydration on the dosing days could mitigate incidence and severity of hypotension as part of CRS. As HAMMER study was not mandating prophylactic hydration before January 2021, the participants who experienced CRS in HAMMER study did not always receive peri-infusion hydration. Based on this learning, hydration and CRS management guidelines have been included in the Phase 2 study protocols.

With respect to PK, SAR444245 exposure increased in an approximately dose-proportional manner in the monotherapy cohorts, and no impact of anti-drug antibody (ADA) on SAR444245 PK could be identified. Also, in the combination cohort, there was no apparent impact of pembrolizumab on the PK of SAR444245.

Differently from native IL-2 and aldesleukin, SAR444245 does not have high potency at the IL-2R $\alpha/\beta/\gamma$ receptor subunit expressed on T regulatory (Treg) cells because the site-specific pegylation blocks IL-2R α engagement and demonstrates high potency at the IL2R β/γ receptor subunit expressed on CD8+ T and natural killer cells (NK). Due to this re-programmed receptor bias, SAR444245 induces proliferation of peripheral CD8+ T and NK cells and less impact on immunosuppressive Treg cells. Therefore, we closely monitored the PDy change of CD8+ T, NK and Treg cells in HAMMER study as supportive information for R2PD selection.

In the SAR444245 monotherapy dose levels (8 μ g/kg, 16 μ g/kg, 24 μ g/kg, and 32 μ g/kg Q3W), the PDy data suggest that a trend for dose-dependent expansion of CD8+ T cells and NK cells has been achieved. In the 8 μ g/kg dose levels, the average increase in peripheral blood CD8+ T cells over baseline at 72 hours post dose was 1.75-fold. For dose levels 16 μ g/kg and 24 μ g/kg, the peripheral blood CD8+ T cell expansion was 2.47 and 4.47-fold at the day 8 post-dose peak of expansion. The day 8 sample timepoint was added after the first 3 participants in the 8 μ g/kg cohort were dosed.

In addition, the average increase in peripheral blood NK cells was 4.22-fold at 72 hours for 8 μ g/kg. The 16 μ g/kg and 24 μ g/kg dose levels resulted in 5.9 and 7.67-fold NK expansion, compared to baseline at the day 8 peak expansion. Among the dose levels tested to date for SAR444245 in combination with pembrolizumab administered using Q3W schedule, we have collected available PDy data for the 8 μ g/kg (n=4) and 16 μ g/kg cohort (n=6), in which the average increase in CD8+ T cells, compared to baseline, is 2.06-fold and 3.71-fold, respectively; and the average increase in NK cells, compared to baseline, is 6.73-fold and 13.43-fold, respectively at the peak expansion day 8. In addition, the comparison of T and NK cell expansion between █ μ g/kg and █ μ g/kg cohorts indicated that the anticipated maximum CD8+ T and NK cells expansion PDy effect may have been achieved at █ μ g/kg cohort. Based on these data, additional quantitative systems pharmacology (QSP) and population PK/PDy models were developed and indicated that the increase of CD8+ T and NK cells was less than proportional with increasing dose, suggesting a flattening of the dose-response curve.

In addition, preclinical studies using human whole blood to assess the induction of cytokines showed no change in cytokine profiles when administering SAR444245 with and without pembrolizumab. This study used SAR444245 concentration ranges that went significantly higher than current clinical dosages (0.2-4.5 μ g/mL) and showed that SAR444245-induced cytokine release in human whole blood was not affected in the presence of pembrolizumab at Q3W schedule.

Considering below, Sponsor proposes to evaluate the clinical benefit of SAR444245 24 µg/kg in this Phase 2 study.

1. SAR444245 monotherapy up to 32 µg/kg Q3W, pembrolizumab combination up to 32 µg/kg Q3W and cetuximab combination 24 µg/kg Q3W are all cleared in HAMMER study.
2. Sustained relevant PDy effect in blood, higher at higher dose, was documented in participants;
3. And overlapping toxicities not suggested by comparing safety data from SAR444245 monotherapy cohort, SAR444245 in combination with pembrolizumab cohort, or SAR444245 in combination with cetuximab cohort. Though theoretically, combining SAR444245 with either pembrolizumab or cetuximab may lead to increase and/or severity of certain AEs (detailed in Section 2.3.1 of the substudies).

